## 6. TRIAL DESIGN

Subjects will be randomized in a 1:1 ratio to the following dose groups:

- Avacincaptad pegol (Zimura™)
- Sham

Note: The international non-proprietary name [INN] of the investigation product, Zimura™, is avacincaptad pegol.

All subjects will be treated as follows:

**Induction Phase:** Administered on Day 1, Month 1, and Month 2 in the following sequence, 14 days apart:

- D0: Avacincaptad pegol 2 mg/eye or Sham
- D14: Avacincaptad pegol 2 mg/eye or Sham

**Maintenance Phase:** Administered every month (Month 3 – Month 17):

- Avacincaptad pegol 4 mg/eye (administered as two injections of avacincaptad pegol 2 mg)
- Sham + Sham

Monthly doses should be targeted for every 30 days from the last monthly visit and must be administered at least 21 days apart.

There will be a final follow-up visit for all subjects at Month 18.

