### **10.2.24 Month 18 Visit ( $\pm 7$ days)/Early Withdrawal**

- Vital Signs
- Protocol refraction and visual acuity (4 meters) using ETDRS chart (OU)
- Tonometry and Ophthalmologic Examination (OU)
- Color fundus photography (FP) (OU)
- Fluorescein Angiography (FA) (OU, transit study eye)
- Spectral Domain Optical Coherence Tomography (SD-OCT) (OU)
- Fundus Autofluorescence (FAF) (OU)
- Microperimetry Testing (OU) (optional assessment)
- Serum pregnancy test (if applicable)
- Laboratory Tests
- 12-Lead ECG

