4.10 Additional Conventions

4.10.1 Analysis Windows

Scheduled Day (Study Day) for analysis windows will be calculated as: Date of visit/assessment – first dose of study drug in this study + 1.

The assignment of visits to analysis will be consistent across all by-visit analysis datasets, and will follow the respective step-by-step algorithm:

1. All assessment visits will be windowed, per the tables below, regardless of scheduled/unscheduled status, injection date, or pre/post-injection status.
2. Baseline derivations will follow the definitions as stated in the SAP.
3. Scheduled visits, that fall into their respective analysis window, will be prioritized over unscheduled visits for assignment to analysis, if multiple visits satisfy this criterion, then next priority will be given to the visit closest to the Scheduled Day as stated per the table will be used.
4. For ADPE/ADIOP only; Assessments flagged for analysis will first have the assessment date match with an exposure date (injection day) and have at least one pre-injection or one post-injection record present. The exceptions to this rule are if the analysis visit is Month 18 or if the analysis visit is Screening.
5. For ADPE/ADIOP only; If there are no scheduled assessments for a particular visit label present then any assessments which match an exposure date (injection day) may be used if there is at least one pre-injection or one post-injection measurement. Unscheduled data which do not match an injection day will not be used for replacement.

For any analysis visit for an assessment for Study Eye, the analysis visit windowing approach will follow that for visits occurring monthly. For any analysis visit for an assessment for Fellow Eye, the analysis visit windowing approach will follow that for visits occurring at either every 3 or 6 months, for further details see the tables below.

There are particular exceptions for ADLB and ADEG. These datasets will contain assessments that are only scheduled to occur twice, at Screening and Month 18. In these cases, all visits (scheduled, unscheduled, early termination) that occur after first study drug exposure will be windowed to either an early termination visit if the study day is < 534 days or Month 18 if the study day is ≥ 534 days.

Listings will include all scheduled, unscheduled, and early withdrawal data.

The definition of visit label and visit windows in reporting are described in the table below.

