For visits occurring monthly (Tonometry (SE), Ophthalmic Examination (SE), Visual Acuity (SE)):

Analysis Visit	Scheduled Day (Study Day)	Analysis Window
Day 1 (D0)	1	1-1
Day 1 (D14)	15	2-23
Month 1 (D0)	30	24-37
Month 1 (D14)	44	38-53
Month 2 (D0)	61	54-68
Month 2 (D14)	75	69-83
Month 3	91	84-107
Month 4	122	108-137
Month 5	152	138-168
Month 6	183	169-198
Month 7	213	199-229
Month 8	244	230-259
Month 9	274	260-289
Month 10	304	290-320
Month 11	335	321-350
Month 12	365	351-381
Month 13	396	382-411
Month 14	426	412-442
Month 15	457	443-472
Month 16	487	473-502
Month 17	517	503-533
Month 18	548	>=534

For visits occurring every 6 months (Vital Signs, Physical Examination):

Analysis Visit	Scheduled Day (Study Day)	Analysis Window
Month 6	183	2-274
Month 12	365	275-457
Month 18	548	>=458

For visits occurring every 9 months (SD-OCT, Microperimetry, FP, FA):

Analysis Visit	Scheduled Day (Study Day)	Analysis Window
Month 9	274	2-411
Month 18	548	>=412

For visits occurring 3/6 months (Tonometry (FE), Ophthalmic Examination (FE), Visual Acuity (FE))

Analysis Visit	Scheduled Day (Study Day)	Analysis Window
Month 6	183	2-229
Month 9	274	230-320
Month 12	365	321-457
Month 18	548	>=458

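### SAP 4.10.1 labels visits by study day with a cut at Day 534, so a completer whose visits run slightly short can have no Month 18 study-eye BCVA and have final labs and ECG labelled early termination

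*SAP*

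**What the plan says.** Protocol Section 6 sets the visit rhythm: "Monthly doses should be targeted for every 30 days from the last monthly visit and must be administered at least 21 days apart". Each monthly visit in Section 10.2 carries a tolerance of 7 days either way. The last one is headed "Month 18 Visit ( $\pm 7$ days)/Early Withdrawal", so completion and early withdrawal share one visit. The protocol does not say whether the 7 days are counted from Day 1 or from the preceding visit.

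SAP Section 4.10.1 defines study day as "Date of visit/assessment – first dose of study drug in this study + 1" and then assigns labels by day: "All assessment visits will be windowed, per the tables below, regardless of scheduled/unscheduled status, injection date, or pre/post-injection status". Scheduled visits get priority over unscheduled ones only when they fall inside their own window. In the monthly table, headed "For visits occurring monthly (Tonometry (SE), Ophthalmic Examination (SE), Visual Acuity (SE", which covers study-eye acuity, tonometry and ophthalmic examination, the last row but one reads "Month 17 517 503-533", and Month 18 is centred on Day 548 with a window from Day 534 onward. Other tables open Month 18 much earlier: Day 458 for vital signs and fellow-eye assessments, and Day 412 for SD-OCT and microperimetry. Labs and ECG after first dose have a separate rule: they "will be windowed to either an early termination visit if the study day is < 534 days", and count as Month 18 from Day 534.

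BCVA change at Month 18 is the first secondary endpoint in the fixed sequence (SAP 2.1). It is estimated with visit as a categorical factor (SAP 4.4.2).

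**The concern.** The protocol and the SAP use different month lengths, and the difference accumulates over 18 visits on the early side of the final window. Labels depend only on the day count, and no rule rescues a completed Month 18 visit that falls before Day 534.

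A completer caught by this has no observed Month 18 value in the BCVA model. The model then has to infer that person's Month 18 outcome from earlier visits, although the acuity was measured at the planned final visit. The Month 18 lab and ECG summaries would also lose someone who finished the trial and place that person's results under early termination.

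**Working it through.** **Reproducing the SAP table.** SAP 4.3.2 uses 30.4375 days per month. Rounding 30.4375 × k gives all 18 monthly scheduled days; for k = 18 it is 547.875, so Day 548. From Month 3 to Month 17, each upper bound is the midpoint of neighbouring scheduled days, rounded up. For Month 17, (517 + 548)/2 = 532.5, so the window ends on Day 533 and Month 18 starts on Day 534.

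**Protocol day for Month 18.** With exact 30-day spacing and the SAP's study-day definition, Month k falls on Day 30k + 1, so Month 18 is 18 × 30 + 1 = Day 541.

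**Early-side margin.** From the SAP's centre it is 548 − 534 = 14 days. From the protocol's target it is 541 − 534 = 7 days.

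**On-target completers.** Day 541 is in the Month 18 window. A final visit a full 7 days early is on Day 534, still Month 18. Every Day 30k + 1 for Months 1 to 17 also lies in its own window.

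**When the label goes wrong.** The final visit must be on Day 533 or earlier, a net lead of 541 − 533 = 8 days. Setting 18d + 1 < 534 gives a mean interval d below 533/18 = 29.61 days.

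**Example: 29-day spacing.** Month 18 falls on 18 × 29 + 1 = Day 523. The same visit is labelled as follows:

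| Assessment | Rule | Label |
|---|---|---|
| Study-eye BCVA | 503–533 | Month 17 |
| Fellow-eye BCVA | ≥458 | Month 18 |
| Vital signs | ≥458 | Month 18 |
| SD-OCT, microperimetry | ≥412 | Month 18 |
| Labs, ECG | <534 | Early termination |

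The nominal Month 17 visit, on 17 × 29 + 1 = Day 494, falls in the Month 16 window, which ends on Day 502. At 28-day spacing the final visit is on 18 × 28 + 1 = Day 505, again labelled Month 17.

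**How often.** The documents give no visit-date scatter, so the shares below are assumptions. They come from simulating 18 intervals of 30 days plus a uniform whole-day deviation.

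| Deviation | Counted from last visit: before Day 534 | Counted from Day 1: before Day 534 |
|---|---|---|
| ±1 day | 1.4% | 0% |
| ±2 days | 10.6% | 0% |
| ±3 days | 18.9% | 0% |
| ±5 days | 28.8% | 0% |
| ±7 days | 34.3% | 0% |

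**Would re-centring be enough?** On 30-day months, Months 17 and 18 fall on Days 511 and 541. The midpoint is (511 + 541)/2 = 526, so Month 18 would open on Day 527. The share missed falls from 18.9% to 4.3% at ±3 days and from 34.3% to 21.7% at ±7 days. Day 523 is still missed.

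**The case against.** The strongest reply is that the mismatch in month length mislabels nobody by itself. A reader might infer that completers who keep to the schedule lose their Month 18 label. The arithmetic shows otherwise, and this part of the reply stands in full.

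Next, the visit tolerance may be anchored to Day 1. Protocol Section 3 calls adherence to prescheduled visits within the window essential. On that reading, with 30-day months, the earliest compliant final visit is Day 534, exactly the SAP bound. The 30-day sentence also concerns doses, and no dose is given at Month 18. This stands as a real ambiguity. However, the target interval runs from the last monthly visit, so the rolling reading is a natural one, and neither document rules it out.

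Third, labelling by elapsed time is a legitimate convention, and the table is consistent with the SAP's definition of 18 months. That is fair for acuity. It does not justify the lab and ECG rule, because early termination describes disposition and a completer has not terminated early.

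Fourth, the true Month 17 value need not be lost. With visits on Days 503 and 532, both fall in Month 17, and the first is nearer Day 517 (14 days against 15), so it is kept. But then the final acuity value is the one left out of the by-visit analysis.

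Finally, the rule ignores treatment arm, BCVA is tested only if the primary succeeds, disposition is summarised separately (SAP 4.2.1), and listings show all visits. All of this limits the damage. No bias between arms has been shown.

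**Conclusion.** The point holds in a limited form. As written, SAP 4.10.1 gives a wrong or missing Month 18 label to a completer who finishes 8 or more days ahead of the 30-day schedule. That requires a mean interval under about 29.6 days and a rolling reading of the ±7-day tolerance. The effect falls on study-eye BCVA, labs and ECG. The primary analysis models time as continuous days (SAP 4.3.2), so its slope does not depend on the monthly table.

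The size is unknown. It is zero if visits are anchored to Day 1 and roughly 1 to 34% of completers under the assumed rolling scatter. A reader might take the upper figures as an expected rate, or convert them into a stated loss of precision for the BCVA contrast. The documents support neither: they give no visit-date variation and no figure for how well earlier acuity predicts Month 18.

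**What to change.** Amend SAP 4.10.1 before unmasking:

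- Give a completer's scheduled Month 18 visit its nominal Month 18 label for study-eye BCVA. Use day windows only for unscheduled and Early Withdrawal visits.
- Classify final labs and ECG as Month 18 or early termination by study disposition (completed or withdrew) instead of the Day 534 cut.
- State how the ±7-day tolerance is anchored, and reconcile the SAP's month length with the protocol's visit target.

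Re-centring the table on 30-day months is not sufficient alone, because a final visit on Day 523 would still be missed. A masked count of completers whose final visit fell before Day 534 would show the actual impact.

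The cost is a SAP text change and dataset programming, with no new data. The small downside is that some Month 18 values would come from slightly shorter follow-up. A sensitivity analysis of BCVA using the current day windows can check whether that matters.

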4.3.3 Supplementary Analysis: Jump to Reference Multiple Imputation

A supplementary analysis will be performed to estimate a slight modification of the Primary Estimand in Section 4.3.1, where instead of the hypothetical strategy, the treatment policy strategy is specified for the ICE of study drug discontinuation. To estimate this estimand, missing outcome data will be imputed using Jump to reference (J2R) multiple imputation (MI) under a missing not at random assumption. J2R MI will result in multiple data sets with complete outcome data. Then, the MMRM model described in Section 4.3.2 will be used to estimate the treatment effect in the multiple imputed data sets. Finally, Rubin's combination rules will be used to obtain a single estimate of the treatment effect and corresponding standard error.

It is worth noting that Rubin's rules can provide conservative inferences (Seaman et al. 2014, Bartlett 2021), e.g., CIs may have significantly greater than 95% coverage probability.

Therefore, jackknife resampling (Wolbers et al. 2022) may also be applied to obtain more accurate frequentist inferences.

The J2R assumption stipulates that the mean outcome trajectory in participants who discontinue study drug in the ACP group will follow the mean outcome trajectory of the Sham group, after the point of discontinuation. This J2R assumption will be used to impute missing outcome data for participants in the ACP group post study drug discontinuation. For participants in the Sham group at all time points and participants in the ACP group up to the time of study drug discontinuation, missing outcome data will be imputed under the missing at random assumption (MAR). The overall MI analysis will be implemented as follows:

1. Parameter estimation model: Let \mathbf{Y}_{Oi} denote the vector of all observed data, and \mathbf{Y}_{Mi} denote the vector of missing observations after the time point of the ICE (denoted by D_i), for participant i .
 - 1) Fit a multivariate normal (MVN) model using \mathbf{Y}_{Oi} , assuming MAR, to data up to the occurrence of the ICE. The MVN model will include pooled geographic region, treatment group, visit (categorical variable), and treatment-visit interaction in the mean function and have a common unstructured variance-covariance matrix across treatment groups.
 - 2) Draw a mean vector and a covariance matrix from the posterior distribution of the fitted MVN model parameters.

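### The two wide SD-OCT and microperimetry windows let an early-withdrawal microperimetry test count as Month 18 when it is up to 136 days early, and may leave some withdrawal scans out of the primary slope model

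*SAP*

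**What the plan says.** **Windows.** SAP 4.10.1 gives the table headed "For visits occurring every 9 months (SD-OCT, Microperimetry, FP, FA" two rows: Month 9, scheduled Day 274, window Day 2-411; and Month 18, scheduled Day 548, window Day 412 onward.

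**Selection.** Step 1 of the same section reads "All assessment visits will be windowed, per the tables below, regardless of scheduled/unscheduled status, injection date, or pre/post-injection status". Step 3 ranks competing records in a window: scheduled before unscheduled, and then "next priority will be given to the visit closest to the Scheduled Day".

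**Early termination.** Only laboratory and ECG records have a label of their own. They are "windowed to either an early termination visit if the study day is < 534 days", and Month 18 from Day 534. Study-eye visual acuity also starts Month 18 at Day 534, in the monthly table.

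**A conflicting sentence.** The text above the tables states: "For any analysis visit for an assessment for Study Eye, the analysis visit windowing approach will follow that for visits occurring monthly". The tables place study-eye SD-OCT and microperimetry elsewhere.

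**Withdrawal visits.** Protocol 10.3 asks that everyone who withdraws have the Early Withdrawal assessments. Protocol 10.2.24 lists SD-OCT and optional microperimetry among them.

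**Models.** The microperimetry model (SAP 4.4.2) uses visit as a category. The primary slope model (SAP 4.3.2) uses continuous days since randomization. The imputation model in SAP 4.3.3, which SAP 4.4.3 reuses for the secondary endpoints, has "visit (categorical variable), and treatment-visit interaction in the mean function".

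**The concern.** In a categorical-visit model the label is the time. A microperimetry test taken at withdrawal on Day 412 enters as an observed Month 18 value, in place of a value that the model would otherwise treat as missing. The Month 18 contrast is the quantity tested third in the fixed sequence of SAP 2.1, and it would mix full and shortened follow-up. The two secondary endpoints in that sequence also define Month 18 differently (Day 534 for BCVA, Day 412 for microperimetry), and no reason is given.

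For SD-OCT the concern is a different one. A withdrawal scan in the months after the Month 9 visit shares a window with the Month 9 scan. If the one-per-window choice governs the primary model, that participant's latest scan is not used, although a slope model in actual days needs no such selection.

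The supplementary jump-to-reference imputation inherits the labels. A short-follow-up scan can be conditioned on as a Month 9 value, or counted as an observed Month 18 value and so not imputed.

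**Working it through.** **1. The plan's own boundary.** At 30.4375 days per month (SAP 4.3.2), 9 × 30.4375 = 273.9, or Day 274, and 18 × 30.4375 = 547.9, or Day 548. The midpoint is (274 + 548)/2 = 411. Month 9 therefore ends on Day 411 and Month 18 starts on Day 412, as the table shows.

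**2. How early a Month 18 value can be.**
- 9-month table: 548 − 412 = 136 days (136/30.4375 = 4.5 months); 412/548 = 75% of the planned time.
- Last day affected by a change to Day 534: 548 − 533 = 15 days.
- BCVA, laboratory and ECG rule: 548 − 534 = at most 14 days.

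**3. Applying steps 1 and 3 to a withdrawal visit on each monthly scheduled day.** The Month 9 record is placed on Day 267, 274 or 281 (Day 274 with the protocol's 7-day tolerance).

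| Withdrawal near | Day | Result under the 9-month table |
|---|---|---|
| Months 1-8 | 30-244 | Labelled Month 9, 244 to 30 days before Day 274 |
| Months 10-13 | 304-396 | Same window as the Month 9 record, which is kept in every case |
| Months 14-17 | 426-517 | Labelled Month 18, 122 to 31 days early |

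The middle row does not depend on whether a withdrawal visit counts as scheduled, which the SAP does not say. If it is unscheduled, the Month 9 visit has priority. If it is scheduled, the Month 9 visit is at most 7 days from Day 274 and is the closer one. The monthly table starts Month 10 at Day 290, so the affected range is about Days 290-411. Microperimetry in that range is dropped in the same way.

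**4. What a left-out scan is worth to one participant's slope.** Under measurement error alone, slope information is proportional to Sxx = Σ(t − mean t)².
- Days 0 and 274: Sxx = 37,538.
- Days 0, 274 and 330: Sxx = 62,371. Share lost = 1 − 37,538/62,371 = 39.8%.
- Days 0, 274 and 411: Sxx = 87,589. Share lost = 1 − 37,538/87,589 = 57.1%.

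Moving the baseline scan to Day −6 gives 39,200 and 90,353 for the Day 411 case, a loss of 56.6%, so the baseline day matters little.

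**5. The same loss with random slopes.** Information is then 1/(B + E/Sxx), where B is the between-participant slope variance and E the error variance. The documents give neither. Assume, for illustration, a slope reliability of 0.8 or 0.9 with scans on Days 0, 274 and 548 (Sxx = 150,152).
- Reliability 0.8: E = 0.25 × 150,152 B = 37,538 B. The variances are 2.000 B without the scan, 1.602 B with Day 330 and 1.429 B with Day 411. Losses are 20% and 29%.
- Reliability 0.9: E = 150,152 B/9 = 16,684 B. The variances are 1.444 B, 1.267 B and 1.190 B. Losses are 12% and 18%.

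**The case against.** **The SD-OCT loss depends on a premise that is not written down.** A reader might infer that the plan discards withdrawal scans from the primary analysis. The documents do not say so. SAP 4.3.2 speaks of values observed at scheduled visits, which suggests window-selected records; Protocol 11.4.3 promises an analysis of all the data available, which does not. Protocol Section 7 names Screening, Month 9 and Month 18 as the timepoints read before lock and is silent on withdrawal scans. The hypothetical strategy for study drug discontinuation (SAP 4.3.1) may exclude some scans whatever the windows do. SAP 4.10.1 keeps every record in the listings. This objection stands, and it makes the SD-OCT part conditional.

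**The 40-57% is an upper bound.** It could be read as the effect on the trial. It is one person's loss with no between-person variation in slope, and the model has participant-level random effects.

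**The laboratory and ECG rule is not an exact precedent.** One might infer that SAP version 2.0 solved this same problem for those data. They are scheduled only at Screening and Month 18, so an early record had no other post-baseline label. Microperimetry has a Month 9 visit and a midpoint cut. The distinction is fair, but it does not explain why BCVA and microperimetry need different Month 18 definitions.

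**Microperimetry is optional, analysed in a subset and last in the sequence.** True, and Day 412 is the worst single day. The estimand's silence on post-discontinuation values applies here too. But no text removes these values, and step 1 windows them all.

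**The study-eye sentence is loose drafting.** Probably so: it refers on to the tables, and the table that names SD-OCT and microperimetry is the more specific. Read literally, it would place these assessments in the monthly windows and largely remove the problem, which is why the two texts must agree.

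**Conclusion.** The microperimetry point holds on the rules as written. A withdrawal test on Days 412-533 is analysed as Month 18 although it is 15-136 days early, and one from Day 2 can be analysed as Month 9. This is a stated rule that weakens a sequence-tested contrast, and the SAP has tighter cut-offs elsewhere.

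The SD-OCT point is conditional. If the primary model uses window-selected records, and if withdrawal scans are graded and allowed by the estimand, a scan on about Days 290-411 after a Month 9 scan is left out. The loss for that person is at most about 40% (Day 330) to 57% (Day 411), and about 12-29% under the assumed reliabilities. The withdrawal rate is not given, so the number of people affected and the effect on the treatment contrast are unknown.

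Two stronger readings are not supported. The primary slope is not mistimed by the labels, because time enters as actual days. Nor is it shown that jump-to-reference understates progression: the labels affect its imputation step, but the model refitted for the primary endpoint again uses continuous time, and the analysis is supplementary.

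The SAP should be changed on this point before unmasking. It does not undermine the primary analysis.

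**What to change.** 1. **Rate-of-change models.** State that they use every graded scan that the estimand allows, including Early Withdrawal scans, at its actual study day, with no one-per-window selection. Confirm that withdrawal scans are graded. Name fundus autofluorescence in the rule, since none of the window tables in SAP 4.10.1 lists it.
2. **Microperimetry and the jump-to-reference visit labels.** Start Month 18 at Day 534, as for BCVA, laboratory tests and ECG. Bound Month 9 with a window already in the SAP, for example Day 230-320 from the fellow-eye table. Label other withdrawal values as early termination.
3. **Study-eye sentence.** Correct it so that it agrees with the 9-month table.

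**Cost.** The work is SAP text, the window table and programming, plus grading of withdrawal scans if that is not already planned. There is also a loss of data: microperimetry values on Days 2-229 and 321-533 leave the categorical-visit model. A participant whose only post-baseline test falls there contributes no post-baseline value, although the subset definition in SAP 4.4.1 still counts that person. Some observed SD-OCT values would be used in the main slope model but not as visit values in the imputation model; the SAP should say so.
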